### 10.1.7 Data Quality Assurance

- All participant data relating to the study will be recorded on electronic CRF unless transmitted to the Sponsor or designee electronically (eg, laboratory data). The Investigator is responsible for verifying that data entries are accurate and correct by physically or electronically signing the CRF.
- The Investigator must maintain accurate documentation (source data) that supports the information entered in the CRF.

- The Investigator must permit study-related monitoring, audits, IRB/IEC review, and regulatory agency inspections and provide direct access to source data documents.
- Monitoring details describing strategy (eg, risk-based initiatives in operations and quality such as Risk Management and Mitigation Strategies and Analytical Risk-Based Monitoring), methods, responsibilities and requirements, including handling of noncompliance issues and monitoring techniques (central, remote, or on-site monitoring) are provided in the Monitoring Plan.
- The Sponsor or designee is responsible for the data management of this study including quality checking of the data.
- The Sponsor assumes accountability for actions delegated to other individuals (eg, Contract Research Organizations).
- Study monitors will perform ongoing source data verification to confirm that data entered into the CRF by authorized site personnel are accurate, complete, and verifiable from source documents; that the safety and rights of participants are being protected; and that the study is being conducted in accordance with the currently approved protocol and any other study agreements, ICH GCP, and all applicable regulatory requirements.
- Records and documents, including signed ICFs, pertaining to the conduct of this study must be retained by the Investigator for 25 years after the signature of the final study report unless local regulations or institutional policies require a longer retention period. No records may be destroyed during the retention period without the written approval of the Sponsor. No records may be transferred to another location or party without written notification to the Sponsor.

### 10.1.8 Source Documents

“Source data” are the data contained in source documents. Source documents are original documents or certified copies, and include, but are not limited to, DCs, medical and hospital records, screening logs, informed consent/assent forms, telephone contact logs, and worksheets.

- Source documents provide evidence for the existence of the participant and substantiate the integrity of the data collected. Source documents are filed at the Investigator’s site.
- Data entered in the CRF that are transcribed from source documents must be consistent with the source documents or the discrepancies must be explained. The Investigator may need to request previous medical records or transfer records, depending on the study. Also, current medical records must be available.

Detailed guidance and information are provided in the Operating Guidelines.

### 10.1.9 Study and Site Start and Closure

Details on which clinical supplies are provided by the Sponsor or the site are described in the Operating Guidelines.

The study start date is considered the date of the first visit planned in the SoA ([Section 1.3](#)) of the first participant.

The Sponsor designee reserves the right to close the study site or terminate the study at any time for any reason at the sole discretion of the Sponsor. Study sites will be closed upon study completion. A study site is considered closed when all required documents and study supplies have been either destroyed or returned to the Sponsor, all samples are shipped to the appropriate laboratories, the center study site has all the documents necessary for archiving and a study site closure visit has been performed along with a Site Close Out Form submitted to the IRB, as required.

The Investigator may initiate study site closure at any time, provided there is reasonable cause and sufficient notice is given in advance of the intended termination.

Reasons for the early closure of a study site by the Sponsor or Investigator may include but are not limited to:

- Failure of the Investigator to comply with the protocol, the requirements of the IRB/IEC or local Health Authorities, the Sponsor's procedures, or GCP guidelines
- Inadequate recruitment of participants by the Investigator
- Discontinuation of further study intervention development

If the study is prematurely terminated or suspended, the Sponsor shall promptly inform the Investigators, the IRBs/IECs, the regulatory authorities, and any contract research organization(s) used in the study of the reason for termination or suspension, as specified by the applicable regulatory requirements. The Investigator shall promptly inform the participant and should assure appropriate participant therapy and/or follow-up.

#### 10.1.10 Publication Policy

Information related to publication policy is described in the Investigator's contract.

### 10.2 Appendix: Clinical Laboratory Tests

- The tests detailed in [Table 10.1](#) will be performed by the site-selected local laboratory.
- Protocol-specific requirements for inclusion or exclusion of participants are detailed in [Section 5](#) of the protocol.
- Additional tests may be performed at any time during the study as determined necessary by the Investigator or required by local regulations.
- A urine human chorionic gonadotropin (hCG) pregnancy test (as needed for women of childbearing potential) will be performed at screening and before each vaccination. Refer to [Section 5.1.1](#) and [Section 5.1.2](#) for pregnancy inclusion criteria.

**Table 10.1: Protocol-required safety laboratory assessments**

Laboratory assessments	Time period for assessment	Parameters
Hematology	
Cohort 1: Screening (between -D04 and -D01) and V02 (D09)
 
Sentinel Cohort & Cohort 2: Screening (between -D04 and -D01), V02 (D09), and V04 (D30)
	
 
• White blood cell (WBC) count with differential: 
 
○ Neutrophils
 
○ Lymphocytes
 
○ Monocytes
 
○ Eosinophils
 
○ Basophils
 
 
 
• Hemoglobin
 
• Platelet count
 

Clinical Chemistry	
Cohort 1: Screening (between -D04 and -D01) and V02 (D09)
 
Sentinel Cohort & Cohort 2: Screening (between -D04 and -D01), V02 (D09), and V04 (D30)
	
 
• Sodium
 
• Potassium
 
• Blood Urea Nitrogen
 
• Creatinine
 
• Glucose (nonfasting)
 
• Aspartate aminotransferase (AST)/Serum Glutamic-Oxaloacetic Transaminase (SGOT)
 
• Alanine Aminotransferase (ALT)/Serum Glutamic-Pyruvic Transaminase (SGPT)
 
• Alkaline phosphatase
 
• Total bilirubin
 
• Direct bilirubin
 
• Total protein
 

Coagulation parameters	
Cohort 1: Screening (between -D04 and -D01) and V02 (D09)
 
Sentinel Cohort & Cohort 2: Screening (between -D04 and -D01), V02 (D09), and V04 (D30)
	
 
• PT
 
• PTT
 
• INR
 

Routine Urinalysis	
Cohort 1: Screening (between -D04 and -D01) and V02 (D09)
 
Sentinel Cohort & Cohort 2: Screening (between -D04 and -D01), V02 (D09), and V04 (D30)
	
 
• Glucose, protein, blood, leukocyte esterase by dipstick
 
• Microscopic examination (if blood or protein is abnormal)
 

Laboratory assessments	Time period for assessment	Parameters
Other Screening Tests	Cohort 1: Screening (between -D04 and -D01), V01 (D01) Sentinel Cohort & Cohort 2: Screening (between -D04 and -D01), V01 (D01), V03 (D22)	Highly sensitive urine human chorionic gonadotropin (hCG) pregnancy test (as needed for women of childbearing potential)*
	Screening (between -D08 and -D01). Results for serology tests obtained within 4 weeks prior to V01 will be accepted.	
 
• HIV antibody
 
• Hepatitis B surface antigen
 
• Hepatitis B core antibody
 
• Hepatitis C antibody
 

	Screening (between -D04 and -D01; All participants)	SARS-CoV-2 antibody

\*To be considered of non-childbearing potential, a female must be post-menopausal for at least 1 year or surgically sterile

It is to be noted that COVID-19 antibody test and blood and urine sampling for safety tests may be performed on the day of enrollment as long as the results to assess exclusion criteria are available prior to enrollment.

Investigators must document their review of each laboratory safety report.

For all participants, laboratory results that could unblind the study will not be reported to investigative sites or other blinded personnel until the study has been unblinded.

## 10.3 Appendix: Adverse Events: Definitions and Procedures for Recording, Evaluating, Follow-up, and Reporting

### 10.3.1 Definition of AE

#### AE Definition

- An AE is any untoward medical occurrence in a patient or clinical study participant, temporally associated with the use of study intervention, whether or not considered related to the study intervention.
- NOTE: An AE can therefore be any unfavorable and unintended sign (including an abnormal laboratory finding), symptom, or disease (new or exacerbated) temporally associated with the use of study intervention.

#### Events Meeting the AE Definition

- Any abnormal laboratory test results (hematology, clinical chemistry, or urinalysis) or other safety assessments (eg, electrocardiogram [ECG], radiological scans, vital signs measurements), including those that worsen from baseline, considered clinically significant in the medical and scientific judgment of the Investigator (ie, not related to progression of underlying disease).
- Exacerbation of a chronic or intermittent pre-existing condition including either an increase in frequency and/or intensity of the condition.
- New conditions detected or diagnosed after study intervention administration even though it may have been present before the start of the study.
- Signs, symptoms, or the clinical sequelae of a suspected drug-drug interaction.
- Signs, symptoms, or the clinical sequelae of a suspected overdose of either study intervention or a concomitant medication. Overdose per se will not be reported as an AE/SAE unless it is an intentional overdose taken with possible suicidal/self-harming intent. Such overdoses should be reported regardless of sequelae.

#### Events NOT Meeting the AE Definition

- Any clinically significant abnormal laboratory findings or other abnormal safety assessments which are associated with the underlying disease, unless judged by the Investigator to be more severe than expected for the participant's condition.
- The disease/disorder being studied or expected progression, signs, or symptoms of the disease/disorder being studied, unless more severe than expected for the participant's condition.
- Medical or surgical procedure (eg, endoscopy, appendectomy): the condition that leads to the procedure is the AE.

- Situations in which an untoward medical occurrence did not occur (social and/or convenience admission to a hospital).
- Anticipated day-to-day fluctuations of pre-existing disease(s) or condition(s) present or detected at the start of the study that do not worsen.

## Other Definitions

### ***Adverse Reaction:***

All noxious and unintended responses to a study intervention related to any dose should be considered adverse reactions (AR).

(The phrase “responses to a study intervention” means that a causal relationship between a study intervention and an AE is at least a reasonable possibility)

### ***Immediate Event/Reaction:***

Immediate events are recorded to capture medically relevant unsolicited systemic AEs (including those related to the study intervention administered) that occur within the first 30 minutes after vaccination.

### ***Medically Attended Adverse Event:***

An MAEE is a new-onset or a worsening of a condition that prompts the participant to seek unplanned medical advice at a physician’s office or Emergency Department. Physician contact made over the phone or by email will be considered a physician office visit for the purpose of MAEE collection. This includes medical advice seeking during the study visit or routine medical care. This definition excludes pediatric check-ups, follow-up visits of chronic conditions with an onset prior to entry in the study, and solicited reactions.

### ***Injection Site Reaction/Administration Site Reactions:***

An injection/administration site reaction is an AR at and around the injection/administration site. Injection/administration site reactions are commonly inflammatory reactions. They are considered to be related to the study intervention administered.

### ***Systemic Adverse Event/Adverse Reaction:***

Systemic AEs are all AEs that are not injection or administration site reactions. They should therefore include systemic manifestations such as headache, fever, as well as localized or topical manifestations that are not associated with the vaccination or administration site (eg, erythema that is localized but that is not occurring at the injection site).

Systemic AEs assessed as related to study intervention are referred as systemic ARs. Solicited systemic reactions occurring during the specified collection period are always considered related to the study vaccine even if there is evidence or alternative etiology.

***Adverse Event of Special Interest:***

An AESI (serious or non-serious) is one of scientific and medical concern specific to the Sponsor's study intervention or program, for which ongoing monitoring and rapid communication by the Investigator to the Sponsor can be appropriate. Such an event might warrant further investigation in order to characterize and understand it. Depending on the nature of the event, rapid communication by the study Sponsor to other parties (eg, regulators) might also be warranted.

***New-Onset Chronic Medical Conditions (NOCMCs):***

NOCMCs are defined as any new ICD-10 diagnosis (10th revision of the International Statistical Classification of Diseases and Related Health Problems) that is applied to the participant during the course of the study, after receipt of the study agent, that is expected to continue for at least 3 months and requires continued health care intervention.

***Reactogenicity/Solicited Reactions:***

A solicited reaction is an "expected" adverse reaction (sign or symptom) observed and reported under the conditions (nature and onset) pre-listed in the protocol and CRF (eg, injection site pain or headache occurring between the day of vaccination and the next 7 days).

By definition, solicited reactions are considered as being related to the study intervention administered.

For injectable vaccines, solicited reactions can either be solicited injection/administration site reactions or solicited systemic reactions.

***Unsolicited Adverse Event/Adverse Reaction:***

An unsolicited AE is an observed AE that does not fulfill the conditions of solicited reactions, ie, pre-listed in the CRF in terms of diagnosis and/or onset window post-vaccination. For example, varicella or a solicited term such as headache starting after the solicited observation period (headache starting on Day 10 post-vaccination in the case where headache occurring between the day of vaccination and the next 7 days is pre-listed in the protocol and CRF as a solicited reaction).

An unsolicited AR is an unsolicited AE that is considered related to study intervention. Unsolicited AEs includes both serious (SAEs) and non-serious unsolicited AEs.

**10.3.2 Definition of SAE**

If an event is not an AE per definition above, then it cannot be an SAE even if serious conditions are met (eg, hospitalization for signs/symptoms of the disease under study, death due to progression of disease).

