**Table 2.1: Potential risks of clinical significance and risk management**

Potential Risk of Clinical Significance	Summary of Data/Rationale for Risk	Risk Management
Investigated Vaccine: SARS-CoV-2 mRNA vaccine		
Anaphylactic reactions	Class-effect for all vaccines (even non-adjuvanted) (24)	Observation period after vaccination for early detection and treatment.  Risk management will also be based on Exclusion criterion E07 (see Section 5.2.1 and Section 5.2.2 ).
Enhanced COVID-19	A theoretical safety issue with coronavirus vaccines is the ability to potentiate the frequency and severity of the clinical manifestations of COVID-19 in vaccinees upon further exposure to wild-type virus (7). The molecular mechanism for this immunopathogenesis is not fully understood. In the context of coronavirus infections, various factors have been suggested as potentially contributing to the phenomenon. These include the epitope targeted, the method of delivery of the antigen, the magnitude of the immune responses, the balance between binding and functional antibodies, the elicitation of antibodies with functional characteristics such as binding to particular Fc receptors, and the nature of the Th response (8) (9) (10).	COVID-19-like illness will be part of the efficacy objective with active and passive surveillance.  It is anticipated that the design of the candidate SARS-CoV-2 mRNA vaccine selected for this study will: 
 
Promote the generation of neutralizing antibodies over binding antibodies, based on data generated with other coronavirus vaccine antigens (5) (6).
 
Produce a favorable T-helper (Th)1/Th2 response, likely predominantly Th1 biased (11).
 
 Individuals with chronic comorbid conditions considered to be associated with an increased risk of severe COVID-19 will be excluded as a strategy to mitigate the potential

Potential Risk of Clinical Significance	Summary of Data/Rationale for Risk	Risk Management
		risk of disease enhancement (25). Taken together, these strategies are designed to mitigate the theoretical risks of immune enhancement of viral infection.
Refer to IB Section 6 for more information regarding potential risks.	Refer to the IB Section 4 for more information regarding the data from previous non-human experience with the LNP.	
Study Procedures		

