### 8.4.3 Halting Rules for Entire Study

An SMT will review the safety data at regular intervals, to identify any new safety signals or safety concerns during the conduct of the study. The SMT is empowered to recommend a pause in both recruitment and/or further vaccination while it investigates any potential signal or concern. Enrollment will be paused during the review and the data will be examined.

Enrollment and/or further vaccination will be paused if the following alert thresholds are identified:

- Any SAEs assessed as related to the vaccine by the Investigator and the Sponsor
- $\geq 2$  participants experiencing ulceration, abscess or necrosis at the injection site that is considered related to the study vaccine by the Investigator and the Sponsor
- For each vaccine group advanced to the Full Enrollment Cohort (ie, potentially Groups 1 to 3 and Groups 5 to 7, N=44 participants per group [Table 4.3]),  $\geq 4$  participants experiencing any Grade 3 AE (systemic reactions lasting for at least 3 days at Grade 3 intensity, unsolicited AEs and/or clinical laboratory abnormality) in the absence of any other etiology
- Events suggestive of vaccine-associated enhanced disease, including:
  - Any death due to SARS-CoV-2 infection

- > 10% of the study population enrolled at any given time is hospitalized due to SARS-CoV-2 infection
- $\geq 3\%$  of study participants  $\geq 50$  years enrolled at any given time are admitted to the ICU due to SARS-CoV-2 infection
- $\geq 3\%$  of study participants 18 to 49 years enrolled at any given time are admitted to the ICU due to SARS-CoV-2 infection

In addition, ad hoc SMT reviews will occur immediately in the event halting rules are met. Case unblinding may be performed if necessary or if any of the halting rules are met.

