### AESIs Related to SARS-CoV-2 Infection and COVID-19 Disease

#### **Immunologic**

- Enhanced disease following immunization

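### The AE and SAE definitions let a site classify a COVID-19 hospitalization or death as a non-SAE, which conflicts with the protocol's own treatment of enhanced COVID-19 as a safety event

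*Protocol*

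**What the plan says.** **Definitions (Protocol 10.3.1 and 10.3.2).**
- The general rule is broad: "An AE is any untoward medical occurrence in a patient or clinical study participant, temporally associated with the use of study intervention", related or not. Conditions first found after the study injection are listed as AEs.
- The list of events that are not AEs includes "The disease/disorder being studied or expected progression, signs, or symptoms of the disease/disorder being studied, unless more severe than expected for the" participant's condition.
- Section 10.3.2 then sets a condition, that the event is not an AE under 10.3.1, and says that such an event "cannot be an SAE even if serious conditions are met (eg, hospitalization for signs/symptoms of the disease under study". Its other example is death from disease progression.

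**Safety text on COVID-19.**
- Table 2.1 names enhanced COVID-19 as a risk: the vaccine might "potentiate the frequency and severity of the clinical manifestations of COVID-19 in vaccinees upon further exposure to wild-type virus".
- Section 8.4.3 pauses the study for any COVID-19 death, when more than 10% "of the study population enrolled at any given time is hospitalized due to SARS-CoV-2 infection", or when at least 3% of either age stratum is in intensive care for it.
- Section 10.5 lists "Enhanced disease following immunization" and a set of COVID-19 complications as AESIs. Footnotes to Tables 1.3 to 1.5 say AESIs are collected as SAEs so that the sponsor hears quickly.

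**Use of the SAE label.** Section 8.4.4 attaches the 24-hour reporting limit to SAEs. Table 3.1 makes SAEs throughout the study a primary safety endpoint, and SAP 5.1.1.2 tabulates them for each intervention group. Neither document states the SAE status of COVID-19 itself.

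**The concern.** The exclusion is wording from a treatment trial, where participants already have the disease and its expected course should not flood the safety database. Here nobody has the disease at entry, and COVID-19 after vaccination is an outcome whose severity the vaccine might change. A site that reads 10.3.1 and then 10.3.2 literally can leave a COVID-19 admission or death out of the SAE records. A site that reads the AE definition broadly will include it. The by-arm SAE counts and the 24-hour reporting would then depend partly on which reading each site takes. The study is first-in-human and has no data monitoring committee (Protocol 9.6).

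**Working it through.** The point rests on definitions, and the plan gives no figure to reproduce. The passages are compared first; arithmetic is then used only to size the backstops.

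**Step 1. Two readings of the definitions.**
- *Not an SAE:* COVID-19 is the studied disease, so it is not an AE (10.3.1), so it cannot be an SAE (10.3.2). The examples in 10.3.2 point this way.
- *An SAE:* COVID-19 in a participant who entered uninfected is a new condition, so it is an AE (10.3.1) and is serious if it leads to admission or death.

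**Step 2. The severity exception does not settle it.** If admission or death always counted as exceeding expectation, the examples in 10.3.2 would be empty. Protocol 2.2 describes symptomatic COVID-19 as running from mild to fatal, with 14% severe and 5% critical in the cited case series, so a site could call an admission expected. The exception is also judged against the participant's condition, and a healthy participant has none that bears on COVID-19.

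**Step 3. Other routes for a serious COVID-19 event.**

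| Route | What it captures | What it leaves open |
|---|---|---|
| AESIs (10.5) | Enhanced disease, ARDS, and listed cardiac, clotting, renal, liver, neurologic and other complications | Pneumonia without ARDS is not listed; enhanced disease needs an undefined judgement |
| Halting rules (8.4.3) | Death, hospitalization and ICU admission by name | Percentage thresholds; the SAE label is not set |
| Illness follow-up (8.2.2, Table 1.6) | Pneumonia as a criterion; hospital course and outcome | No 24-hour limit |
| MAAEs (10.3.1, 8.4.10) | New conditions prompting unplanned medical advice; COVID-19 not excluded | Ordinary AE process; a strict reader may require an AE first |
| Harm test (SAP 5.1.1.2) | Split of COVID-19 cases, vaccine versus placebo | Counts cases, not severity |

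**Step 4. Size of the two numerical backstops at planned enrollment.** Inputs are Protocol 1.1 and Table 4.3: 25 + 308 = 333 planned and 75 + 308 = 383 at most; 25 + 140 = 165 aged 18-49 and 168 aged 50 or over; 6 × 44 = 264 vaccine and 2 × 22 = 44 placebo recipients in the Full Enrollment Cohort.
- Hospitalization rule, more than 10%: 0.10 × 333 = 33.3, so 34 participants; 0.10 × 383 = 38.3, so 39.
- ICU rule, at least 3%: 0.03 × 165 = 4.95, so 5; 0.03 × 168 = 5.04, so 6.
- Death rule: 1.
- Harm test, one-sided 0.05. In the extreme case where all n cases are in vaccine arms, p = (vaccine share)^n. With 264/308 = 0.857, n = 19 gives 0.053 and n = 20 gives 0.046, so 20 cases are needed. With the Initial Sentinel Cohort, 289/333 = 0.868: n = 21 gives 0.051 and n = 22 gives 0.044, so 22 are needed.

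Fewer events trigger the percentage rules early in enrollment. At full planned enrollment, one non-ICU COVID-19 admission without a listed AESI triggers neither backstop.

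**The case against.** A reader might infer that a COVID-19 hospitalization or death is, as written, not an SAE. The documents do not support that flat statement. Section 10.3.2 applies only to events that are not AEs, 10.3.1 makes an exception for unexpected severity and counts new conditions as AEs, and references to disease progression presuppose an existing disease that no participant has. This part of the objection stands.

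A reader might also infer that enhanced COVID-19 goes unmonitored, or that serious COVID-19 cannot be counted by arm. Neither follows. The AESI list extends well beyond ARDS, to myocarditis, pulmonary embolus, kidney and liver injury and even loss of smell or taste, so many admissions could qualify. Illness follow-up records hospitalization and outcome without reference to AE status. MAAEs are themselves a primary safety endpoint tabulated under SAP 5.1.1.2. These routes stand, and they make a repair possible.

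They do not settle the SAE label. They also have limits at the final analysis. The efficacy endpoints in SAP 4.4.4 carry no severity measure, and SAP 5.1.2.4 drops the vaccine-efficacy and correlates analyses. After vaccination ended on 27 September 2021, SAP sections 1 and 5.7 name SAEs, AESIs, MAAEs, pregnancy and vaccine receipt as still monitored. COVID-19-like-illness surveillance is not named there, although that does not show it stopped.

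Finally, with vaccination over and follow-up cut to 6 months, rewording the definitions can change little prospectively. That is fair, and it moves the weight of the remedy to the pre-lock check.

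**Conclusion.** The concern holds as an unresolved inconsistency. Sites can classify as a non-SAE either a COVID-19 hospitalization without a listed AESI or a COVID-19 death. The first then has no assured 24-hour route. The second triggers a pause under 8.4.3, but its SAE status is unsettled. A primary safety endpoint can therefore depend on site interpretation.

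The number of affected events cannot be stated. A reader might multiply an assumed attack rate by the severity split in Protocol 2.2, or suppose that most of the trial's SAEs are at stake. The documents do not support either: they give no attack rate, the split comes from a general case series while 5.2 excludes people at raised risk of severe disease, and enrollment was stopped early. The count could be zero. The backstop figures above assume full planned enrollment. No sample-size, power or alpha figure is affected.

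**What to change.** **Wording.** Reconcile 10.3.1 and 10.3.2 with Table 2.1, 8.4.3 and 10.5. Remove the studied-disease item from the events that are not AEs, and remove the hospitalization example in 10.3.2. The companion example of death from progression raises the same question and should go with it. State that COVID-19 after vaccination that meets any seriousness criterion is recorded as an SAE. Limit the sentence to serious events, because 8.4.4 collects non-serious unsolicited AEs only to D22 after each vaccination and that window should stay as it is.

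**Data.** Before final database lock, cross-check the COVID-19-like-illness forms, MAAEs and safety-call records for hospitalization, ICU admission or death against the SAE dataset. Report any omitted serious COVID-19 event by arm, using the SAP's existing rule (4.4.1.3) that lists separately events starting on or after receipt of a non-study COVID-19 vaccine.

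**Cost.** A small reconciliation of data already collected, and possibly a few more SAE records.
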